8.2.3. Safety analysis

8.2.3.1. Adverse reactions

- All adverse reactions**

Number and proportion of patients with adverse reactions will be tabulated by SOC and PT.

- Serious adverse reactions**

Number and proportion of patients with serious adverse reactions will be tabulated by SOC and PT.

- Details of adverse reactions**

Number and proportion of patients with adverse reactions will be tabulated by SOC and PT for each of the following items.

- Seriousness [Serious, non-serious]
- Expected/unexpected [expected, unexpected]
- Number of days to onset [≤ 4 weeks, >4 to ≤ 13 weeks, >13 weeks]
- Action taken [discontinuation, dose interruption or reduction, dose increase]
- Outcome [not recovered, recovered with sequelae, recovering, resolved/recovered, unknown]

If the same adverse reaction (the same PT) occurs more than once in the same patient, tabulation of the number of patients experiencing the adverse reactions will be handled as follows.

- Seriousness: Serious if both serious and non-serious reactions occurred
- Expected/unexpected: Unexpected if both expected and unexpected reactions occurred
- Number of days to onset: Number of days to onset of the first reaction
- Action taken: If more than one action were taken, select one action in the following order of priority: discontinuation, dose interruption or reduction, dose increase, none
- Outcome: Outcome of the reaction lastly occurred in the patient

- Major investigation items**

Number and proportion of patients will be calculated for the following major investigation items.

- Peripheral edema and edema-related events*^a
*: Adverse events of the cardiovascular and respiratory systems will also be checked.
- Dizziness, somnolence, loss of consciousness, syncope, and potential for accidental injury
- Vision-related events

Furthermore, number and proportion of patients with major investigation items will be tabulated for each SOC and PT by seriousness, action taken and outcome.

For “peripheral edema and edema-related events”, number and proportion of patients with events will be tabulated by presence or absence of weight increase. Two types of definitions of patients with weight increase are used: 1) those with “weight increased (MedDRA PT)” reported as an adverse reaction; 2) those with body weight increased by 7% or more from baseline at least once. Number and proportion of patients with adverse reactions will be tabulated for each SOC and PT by presence or absence of peripheral edema. In addition, number and proportion of patients with the following adverse reactions will be tabulated by presence or absence of peripheral edema to evaluate the relationship between peripheral edema and cardiovascular and respiratory events.

- Events coded to the MedDRA PT “arrhythmia”, “atrial fibrillation”, “cardiovascular disorder”, “cardiac failure congestive”, “hypertension”, “hypotension”, “palpitations”, “tachycardia”, or “dyspnoea”
- Events coded to the MedDRA SOC “Cardiac disorders”, “Vascular disorders”, or “Respiratory, thoracic and mediastinal disorders”

For “dizziness, somnolence, loss of consciousness, syncope, and potential for accidental injury”, number of days to onset will be tabulated using more specific categories (≤ 4 weeks [1 to 28 days], 1 to 7 days, 8 to 14 days, 15 to 21 days, 22 to 28 days; >4 weeks [≥ 29 days], >4 to ≤ 13 weeks, >13 weeks). In addition, number and proportion of patients with adverse reactions will be tabulated by factor specified in Section 5.4. Tests specified in Section 8.1.3 will be performed to evaluate the relationship between patient demographics, etc. and development of adverse reactions.

Moreover, the median number of days to onset will be tabulated for the following adverse reactions.

- Dizziness
- Somnolence

^a: Occurrence of cardiovascular and respiratory events will be examined in patients with peripheral edema and edema-related events.

- Peripheral edema and edema-related events
- **Pancreas-related events, thyroidal function-related events, change in appetite and activity-related events, suicide-related events, withdrawal symptom and rebound phenomenon-related events, and skin disorder-related events**

Number and proportion of patients will be calculated for each event.

- **Patients with special background**

Number and proportion of patients with adverse reactions and serious adverse reactions will be calculated by SOC and PT in the following subgroups and other patients.

- Elderly patients
- Pediatric patients
- Patients with renal impairment
- Patients with hepatic impairment

Patients with renal impairment are defined as those with “Renal impairment: yes” or creatinine clearance of less than 60 mL/min.

- **Relationship between dosage and administration and development of adverse reactions**

In order to evaluate the relationship between dosage and administration and development of adverse reactions, number and proportion of patients with adverse reactions will be tabulated by SOC and PT for patients whose creatinine clearance and the initial daily dosage are ≥ 60 mL/min and 150 mg, respectively, and patients whose creatinine clearance and the initial daily dosage are ≥ 30 to < 60 mL/min and 75 mg, respectively.

- **Relationship between prior and concomitant medications and development of adverse reactions**

In order to evaluate the relationship between the drug class of prior or concomitant medications and adverse reactions, number of patients with adverse reactions will be tabulated for each PT by target disease (i.e., diagnosis of neuropathic pain) and drug class of prior or concomitant medications. However, concomitant medications used after the initial onset of the event will be excluded from tabulation. For target disease, diseases with number of patients analyzed of approx. 100 or more will be examined.

- **Occurrence of adverse reactions by inclusion in/exclusion from the safety analysis set**

A listing of adverse reactions in patients excluded from the safety analysis set will be prepared. Moreover, number of patients with adverse reactions will be tabulated by SOC and PT.

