## 1 Objectives

The objective of this survey is to evaluate the safety and efficacy of the product in routine clinical practice. In addition, efforts will be made to collect information on the incidence of previously known and unknown adverse reactions that will occur under actual use conditions during the survey period. At the same time, the necessity of conducting a special investigation or a post-marketing clinical study will be evaluated.

The following events will be evaluated as major investigation items;

- Peripheral edema and edema-related events\*
- Dizziness, somnolence, loss of consciousness, syncope and potential for accidental injury
- Vision-related events

\*: Adverse events of the cardiovascular and respiratory systems will be also checked.

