**(2) Clinical findings**

The following information will be entered about the clinical findings before the start of treatment (including the first day of treatment) and during the period from the start of treatment to the day of safety evaluation. In cases where treatment has been completed or discontinued before Week 13, the data at the time of completion (discontinuation) of treatment will be entered. If the investigator considers that the change in any of the clinical findings from the pre-treatment status is abnormal, it will be reported as an adverse event.

**(2)-1 Information before the start of treatment (including the first day of treatment) and during the period from the start of treatment to the day of safety evaluation**

[Presence/absence of peripheral edema or edema in general]\*, [Presence/absence of dizziness, somnolence, loss of consciousness, syncope and potential for accidental injury], [Presence/absence of ophthalmological abnormalities], [Presence/absence of suicidal ideation (including suicide attempt and suicide after start of treatment)], [Presence/absence of pathologic changes in appetite and activity]

**Supplementary note\***: In cases where peripheral edema or edema in general is found, adverse events of the cardiovascular and respiratory systems also need to be checked. If any clinically significant change from the pre-treatment condition is found, it should be entered in detail in the field for adverse events.

**(2)-2 Information in cases of completed (discontinued) treatment with the product (information on the day of safety evaluation following 7-day period after the day of discontinuation [including Day 7 of this period])**

[Presence/absence of withdrawal symptom/rebound phenomenon]

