## 6.9 Major investigation items

The following events should be evaluated as major investigation items in this survey.

- [1] Peripheral edema and edema-related events
 

Information will be collected about the presence/absence of events related to peripheral edema and the course of patients before and after the onset of events. The situations on development of these events will be analyzed by means of factor analysis, including analysis of the site affected, dose of the product, concomitant therapy, background variables, etc. The package insert gives precautions on congestive heart failure in patients presenting symptoms related to edema. In 30 overseas placebo-controlled studies, the incidence of hypertension and dyspnea was higher in the patients developing peripheral edema than in patients free of peripheral edema, although the incidence of the other events did not differ markedly between these two groups. In view of these facts, information on cardiac function and the incidence of adverse events of the respiratory system will be also collected.
- [2] Dizziness, somnolence, loss of consciousness, syncope and potential for accidental injury
 

Information will be collected about the presence/absence of events related to dizziness, somnolence, loss of consciousness, syncope and potential for accidental injury and the course of patient's condition before and after the onset of events. The situations on development of these events will be analyzed by factor analysis, including analysis of the dose of the product, concomitant therapy, background variables and so on.
- [3] Vision-related events
 

Information will be collected about the presence/absence of events related to the eyes and the course of patient's condition before and after the onset of events. The situations on development of the events will be analyzed by factor analysis, including analysis of the dose of the product, concomitant therapy, background variables and so on.

Patients developing adverse events included in the major investigation items will be

separately investigated in detail if the sponsor deems it necessary.

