### 7.2 Methods of analysis

#### 7.2.1 Safety analysis

In the safety analysis set, the status of onset of adverse reactions and incidence of adverse reactions (percentage of patients developing adverse events for which the causal relationship with the product cannot be ruled out) will be set as primary analysis items. The factors affecting the incidence of adverse reactions will be also analyzed, for example, the incidence of adverse events will be summarized for each of the factors including background variable.

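### Accident-related events, and the comparison of cardiovascular and respiratory events by edema status, get dedicated outputs only as adverse reactions, although the plan names adverse events

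*SAP*

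**What the plan says.** **Two levels of event.** SAP 6.1 defines adverse reactions as events that the investigator or the sponsor judges related to the drug, and adverse events as events of any cause.

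**Accidents and suicide.** SAP 6.1 defines both groups by an SMQ. It says that accident-related events are to be assessed as adverse events, and that suicide-related events are to be assessed at that level too. The grouped counts at the end of the major-item text in SAP 8.2.3.1 cover six endpoints. Suicide-related events are among them; accident-related events are not. SAP 8.2.3.2 tabulates adverse events by SOC and PT, overall and by seriousness, with no SMQ-level count. Section 9 has one accident-specific listing, and it is of adverse reactions.

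**Edema item.** Protocol section 1 says "Adverse events of the cardiovascular and respiratory systems will be also checked"; SAP 2.2, 6.1 and 8.2.3.1 repeat this. The note in Protocol 6.4 (2) tells investigators that where edema is found, "adverse events of the cardiovascular and respiratory systems also need to be checked". Protocol 6.9 gives a reason: in overseas placebo-controlled studies, "the incidence of hypertension and dyspnea was higher in the patients developing peripheral edema than in patients free of peripheral edema".

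SAP 8.2.3.1 plans two tables split by edema status. One covers everything: "Number and proportion of patients with adverse reactions will be tabulated for each SOC and PT by presence or absence of peripheral edema". The other covers a named cardiovascular and respiratory list: "number and proportion of patients with the following adverse reactions will be tabulated by presence or absence of peripheral edema to evaluate the relationship". A footnote adds: "Occurrence of cardiovascular and respiratory events will be examined in patients with peripheral edema and edema-related events".

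**The concern.** For accidents, a listing restricted to related events drops those judged unrelated, while the SAP's own endpoint definition includes them. A fall or road accident is easily put down to something other than the drug, so the level matters. There is also no planned number of patients with any accident-related event.

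For edema, the protocol motivates the check by an incidence comparison between patients with and without edema. The SAP plans that comparison, but only on events that passed a causality judgement, in a survey with no comparison group. If an assessor is readier to call a cardiovascular event drug-related when the patient also has edema, the judgement itself shapes the association in the table. No planned table shows the comparison without that filter.

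**Working it through.** No figure in the plan bears on this point, so the main check sets the stated level of each item beside its planned outputs.

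**1. Level named against outputs planned**

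| Item | Level named | Dedicated output | Level of that output |
|---|---|---|---|
| Accident-related events (SMQ) | adverse events (SAP 6.1) | one listing (Section 9); no grouped count in 8.2.3.1 or 8.2.3.2 | adverse reactions |
| Suicide-related events (SMQ) | adverse events as well (SAP 6.1) | grouped count (8.2.3.1) | under the adverse reactions heading |
| Cardiovascular and respiratory events, edema item | adverse events (Protocol 1; SAP 2.2, 6.1, 8.2.3.1) | two edema-split tables (8.2.3.1); none in 8.2.3.2 | adverse reactions |

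Euphoric mood-related events are also missing from the grouped counts, but they are a single PT, so the SOC/PT tables already give their count.

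**2. Can the general adverse event table replace the accident count?** If the SMQ covers PTs with patient counts n1, ..., nk, the number of patients with any of them lies between max(ni) and the sum of the ni. It equals the sum only if no patient has two of the PTs. The figure can be derived from patient-level data, but not from the planned table.

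**3. Causality filter on the events (illustration; all shares assumed).** Let s1 and s0 be the shares of affected patients, with and without edema, who have an event judged related. Then

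shown risk ratio = all-cause risk ratio × (s1/s0).

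- equal shares: × 1.00
- 0.55/0.50: × 1.10
- 0.60/0.50: × 1.20
- 0.70/0.50: × 1.40
- 0.50/0.60: × 0.83
- 0.80/0.40 (extreme): × 2.0

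If s0 is at least 0.80, the factor cannot exceed 1/0.80 = 1.25.

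**4. Causality filter on edema status (illustration).** This applies if edema status means an adverse reaction. Take the target of 3400 patients (Protocol 3) and assume 200 with edema, with event risks of 20/200 = 10% and 160/3200 = 5%; the ratio is 2.0. Patients whose edema is judged unrelated move to the group without edema.

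- 5 of 20 with an event and 45 of 180 without (25% in both): (15/150)/(165/3250) = 1.97
- 6 of 20 and 36 of 180 (30% and 20%): (14/158)/(166/3242) = 1.73
- 10 of 20 and 36 of 180 (50% and 20%): (10/154)/(170/3246) = 1.24
- 4 of 20 and 54 of 180 (20% and 30%): (16/142)/(164/3258) = 2.24

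The shift can go either way and is small when the judgement does not depend on the other event.

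**5. What the other planned tables show.** Setting the reaction table in 8.2.3.1 beside the event table in 8.2.3.2 shows, for each SOC and PT, how many patients the filter removes overall. It does not separate patients with edema from those without, so s1 and s0 cannot be recovered from it.

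**The case against.** **Adverse reactions are the survey's primary safety item.** Protocol 7.2.1 says so, and reaction-level edema tables follow from that choice. This stands: the existing tables are legitimate and should stay. A reader might look for support for all-cause tables in the remark there that "the incidence of adverse events will be summarized for each of the factors including background variable". That sentence opens with factors affecting adverse reactions and does not mention edema, so it gives none.

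**Checking is not tabulating.** A reader might infer that the documents promised an all-cause table by edema status and then left it out. They did not: the wording commits to checking and collecting, and the SAP footnote speaks of examining events without specifying a table. The argument is narrower. The SAP itself chose to evaluate this relationship in tables, and did so at one level only.

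**The filter is broad.** A reaction is any event whose causal link cannot be ruled out (Protocol 7.2.1), and under SAP 6.1 a judgement by either the investigator or the sponsor is enough. Few events may be removed, and the distortion may be slight. This is fair, and the documents do not settle it.

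**Edema status is not really open.** The stronger claim that it is undefined goes too far. The tables stand under the adverse reactions heading, the wider edema group is defined through the European risk management plan, and an adverse reaction is the most natural reading. The survey form does record "Presence/absence of peripheral edema or edema in general" as a clinical finding, but abnormal changes there are to be reported as adverse events. What remains is missing detail: the terms and event type behind the split are not restated, the footnote uses the wider group, and the same paragraph does spell out two definitions of weight increase.

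**Accident events are not hidden.** Individual PTs appear in the all-cause tables and in the listing of patients with adverse events, and potential for accidental injury is part of a major item. That is partial visibility. It gives no patient count for the SMQ, and it does not reconcile the dedicated listing with SAP 6.1.

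**Conclusion.** The point holds as a minor one, in three parts.

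- **Accidents and suicide.** The accident listing conflicts with SAP 6.1, and no SMQ-level patient count is planned for accidents. The suicide-related count is placed only under adverse reactions, although SAP 6.1 also calls for adverse events. This rests on the text alone.
- **Edema comparison.** The edema-split tables count only events judged related, and no all-cause counterpart is planned. The documents do not show that the association will be distorted. They give neither the shares judged related nor the frequency of edema, so apart from the 3400 target every input to the illustrations is an assumption, and equal shares on the event side change nothing.
- **Edema terms.** This is a subsidiary clarification, not a gap of its own.

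SAP 4.1 describes testing in this survey as exploratory, so the consequence is limited to how these safety tables are read.

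**What to change.** 1. **Section 9:** change the accident-related listing to adverse events, with the causality judgement shown for each.
2. **SAP 8.2.3.2:** add the number and proportion of patients with accident-related adverse events (SMQ level), and the same for suicide-related adverse events.
3. **SAP 8.2.3.1:** beside the cardiovascular and respiratory reaction table by edema status, add an all-cause version in which edema status is also set from all-cause events. State which terms and which event type define edema status in each version.
4. **Optional:** an all-cause version of the full SOC/PT table by edema status.

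The cost is a few more tables and one definition, from data already collected. All-cause counts will be higher and less specific to the drug, which is why the reaction tables should stay beside them.

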## 5.4 Observation period

The observation period will start on the first day of treatment with the product (Day 1) and last until Week 13 (Day 91). However, in cases where treatment has been completed or discontinued before Week 13, observation will be continued until completion (discontinuation) of treatment, and follow-up will be made for one week (7 days) after completion (discontinuation) of treatment. During this survey, safety will be evaluated on the day of the first visit after the end of the observation period (including the last day of the observation period), as a rule. In cases where treatment has been completed or discontinued, safety will be evaluated until the day of the first visit following 7-day period after the completion (discontinuation) of treatment, and safety information will be collected for this period.

**Supplementary note:** Completion of treatment means cases where further treatment with the product is judged unnecessary because of achievement of the purpose of treatment set at the start of treatment (e.g., cure of target diseases).

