8.2.3.3. Other endpoints

- **Body weight**

Summary statistics specified in Section 8.1.1 will be calculated by time point as defined in Appendix 1 for measurements and their changes from baseline.

Number and proportion of patients with the following adverse reactions will be tabulated for patients whose body weight increased by 7% or more from baseline at least once and other patients.

- Abnormal glucose tolerance-related events: Events coded to the MedDRA HLGT “glucose metabolism disorders (incl diabetes mellitus)” or the MedDRA HLT “carbohydrate tolerance analyses (incl diabetes)”
- Dyslipidemia-related events: Events coded to the MedDRA HLGT “lipid metabolism disorders” or “lipid analyses”
- Events coded to the MedDRA PT “arrhythmia”, “atrial fibrillation”, “cardiovascular disorder”, “cardiac failure congestive”, “hypertension”, “hypotension”, “palpitations”, “tachycardia”, or “dyspnoea”
- Events coded to the MedDRA SOC “Cardiac disorders”, “Vascular disorders”, or “Respiratory, thoracic and mediastinal disorders”

- **Laboratory parameters**

Summary statistics specified in Section 8.1.1 will be calculated by time point as defined in Appendix 1 for laboratory parameters and their changes from baseline.

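### Reactions are compared by peripheral edema and by 7% weight gain, both of which arise during follow-up, with no allowance for unequal observed time, so the proportions are not comparable

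*SAP*

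**What the plan says.** SAP 8.2.3.1 plans two edema tables. The general one reads: "Number and proportion of patients with adverse reactions will be tabulated for each SOC and PT by presence or absence of peripheral edema". The second takes a named list of cardiovascular and respiratory terms, plus three whole system organ classes: "number and proportion of patients with the following adverse reactions will be tabulated by presence or absence of peripheral edema to evaluate the relationship" of edema to such events. The SAP does not define presence or absence further. The natural reading is whether edema occurred at any time in the survey.

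SAP 8.2.3.3 (Body weight) is explicit. Glucose, lipid, cardiovascular and respiratory reactions "will be tabulated for patients whose body weight increased by 7% or more from baseline at least once and other patients".

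Neither section conditions on the order of onset, uses time at risk, or fixes a common observed period. No test, risk ratio or interval is planned for these splits.

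Observed time varies by design. Under Protocol 5.4, "in cases where treatment has been completed or discontinued before Week 13, observation will be continued until completion (discontinuation) of treatment", with a further 7 days of follow-up. SAP Appendix 1 gives body weight two post-baseline windows (Day 2-60 and Day 61-137), and SAP section 7 does not impute missing weights.

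Protocol 6.9 says that information will be collected on "the course of patients before and after the onset of events" for edema. Elsewhere in 8.2.3.1 the SAP does apply an order rule: concomitant drugs first used after the initial onset of an event are left out of the drug-class table.

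**The concern.** A patient observed for 13 weeks has more chance to develop edema, to be weighed 7% above baseline, and to have any other reaction than a patient who stops in week 2. Sorting patients by what happened during follow-up therefore also sorts them by how long they were watched. The group with edema or gain and the group without then differ in observed time, and their reaction proportions differ even if edema or gain has no bearing on the reaction. The distortion can also run the other way: if edema often leads to stopping, the edema group is the one cut short.

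Weight gain has an added problem. A patient with no post-baseline weight cannot be shown as a gainer and, as worded, falls among the other patients.

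The edema table is stated to evaluate a relationship, and Protocol 6.9 gives the clinical reason: the package-insert precaution on heart failure, and more hypertension and dyspnea among edema patients overseas. The survey's results go into the reexamination application. A reader of the planned table could not tell how much of a difference reflects time observed, nor whether the reactions came before or after the edema.

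**Working it through.** **Plan's own figures.** The documents give no figure for these comparisons. The sample-size figures reproduce: 1 - (1 - 0.001)^3400 = 0.967, against 97% stated, and 3400 x 0.067 = 227.8, against 227 stated. They do not bear on this point.

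**Inputs.** From the documents: observation to Day 91, or to stopping plus 7 days; target 3400 patients. Assumed, because the documents do not give them: edema or gain risk 5-15%, reaction risk 1-5%, stopping before Day 91 in 0-50%.

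**Step 1: why the ratio moves.** Let T be a patient's observed time. Let edema and the reaction be independent, with small constant rates m and r.
- Reaction proportion among edema patients: mean(rT x mT) / mean(mT) = r x mean(T²) / mean(T).
- Among the others: about r x mean(T).
- Ratio: about mean(T²) / mean(T)², which is 1 plus the squared coefficient of variation of T.

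The order of the two events does not appear in this expression. If T is the same for everyone, the ratio is 1.

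**Step 2: numbers.** Early stoppers are spread evenly over Days 1-28 or Days 28-91, with 7 days added. Their mean T is 14.5 + 7 = 21.5 and 59.5 + 7 = 66.5. Their mean T² is 21.5² + 27²/12 = 523 and 66.5² + 63²/12 = 4753. Completers have T = 91 and T² = 8281. For 30% early, 20% later and 50% completing:
- mean(T) = 0.3 x 21.5 + 0.2 x 66.5 + 0.5 x 91 = 65.25
- mean(T²) = 0.3 x 523 + 0.2 x 4753 + 0.5 x 8281 = 5248
- ratio = 5248 / 65.25² = 1.23

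The same formula for the other mixes, beside a simulation of 3 million patients per scenario (edema 10%, reaction 2%, no true relation):

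| Stopping (Days 1-28 + Days 28-91) | Formula | Simulated ever/never ratio | Time-split rate ratio |
|---|---|---|---|
| 0% | 1.00 | 1.00 | 1.00 |
| 10% + 10% | 7152.4 / 81.6² = 1.07 | 1.08 | 0.99 |
| 20% + 20% | 6023.8 / 72.2² = 1.16 | 1.18 | 1.05 |
| 30% + 20% | 1.23 | 1.25 | 0.98 |

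At 50% stopping the simulated ratio stays at 1.22-1.25 across edema risks of 5-15% and reaction risks of 1-5%. The time-split column treats edema as a state that begins at its onset and divides reactions by patient-days in each state. It stays at 0.97-1.05 in every scenario run.

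**Step 3: the other direction.** With 8% edema, 3% reactions and 30-50% stopping, letting half of edema cases stop within 14 days gives a ratio of 0.72-1.04. If the reaction itself ends treatment, the ratio falls to 0.55-0.74 (edema 10%, reaction 2%, other stopping 0-50%).

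**Step 4: weight gain.** With 8% gain, 3% reactions and 30-50% stopping, the ratio is 1.15-1.39.

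**Step 5: event order.** In the no-stopping row of the table, half of the patients with both events had the reaction first, and the ratio was still 1.00.

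**Step 6: expected counts.** 3400 x 0.08 = 272 edema patients, and 272 x 0.03 = 8.2 with the reaction. Among the other 3128, 3128 x 0.03 = 93.8. The standard error of the log risk ratio is sqrt(1/8.16 - 1/272 + 1/93.84 - 1/3128) = 0.359. A true ratio of 1 then has a 95% interval of exp(±1.96 x 0.359) = 0.49 to 2.02. A ratio of 1.25 is 8.16 x 0.25 = 2 extra patients, and 1.39 is 8.16 x 0.39 = 3.

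**The case against.** The strongest reply is that these are descriptive tables. SAP 4.1 calls testing exploratory, 4.2 has no decision rule, and no test or interval is planned here. With about 8 patients expected to have both events, chance outweighs a distortion worth two or three patients. The edema split also mirrors the overseas comparison in Protocol 6.9 that motivated it, so keeping that form is defensible. All of this stands. It is why the planned counts should stay and why the point concerns interpretation.

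Several stronger readings are tempting but are not supported:
- **That counting reactions that preceded the edema creates a false association.** Under equal follow-up it does not (Step 5). Order matters for what the table can tell the reader, not for the ratio by itself.
- **That glucose and lipid reactions are singled out for comparison by edema.** Section 8.2.3.3 defines those groups ("Abnormal glucose tolerance-related events: Events coded to the MedDRA HLGT"; "Dyslipidemia-related events: Events coded to the MedDRA HLGT") and splits them by weight gain only. By edema they appear only within the general table.
- **That Protocol 6.9 requires a time-split table.** Its sentence on the course before and after onset concerns what is collected.
- **That nothing else addresses the question.** A footnote in 8.2.3.1 plans to examine cardiovascular and respiratory events in edema patients, and the SAP listings would allow case review. Still, no planned table sets out order or observed time.

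It may also be said that edema tends to come early: Protocol 5.3 reports the highest incidence of edema and dizziness early in treatment. That weakens the edema effect. With edema 30% or 70% concentrated in the first 28 days and not causing stopping, the ratio was 1.03-1.24. It does not remove the problem.

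**Conclusion.** The concern holds as a limit on interpretation. Patients are grouped by a state that arises after treatment starts, and observed time is unequal, so the proportions in the two groups are not comparable. With no true relation and an assumed 30-50% stopping early, the ratio is about 1.2-1.4, nearer 1 if edema is concentrated early. For edema it is about 0.7-1.05 if edema often leads to stopping. The direction is not fixed, so a reader cannot correct for it by eye. All these sizes rest on assumed edema, gain, reaction and stopping rates.

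Two parts do not depend on assumed rates: the tables take no account of observed time, and they cannot show whether a reaction came before or after the edema. For edema, ever versus never is the natural reading of the SAP, not its explicit wording; for weight gain it is explicit. A reader might infer a confirmatory error, but the documents do not support that, because the tables are descriptive and the expected counts are small.

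**What to change.** Keep the planned counts and add beside them, from dates already collected:

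- **(a) Edema (8.2.3.1):** reactions per patient-days before (or without) edema and after its onset, with edema as a time-varying state.
- **(b) Edema, order:** the number of edema patients whose cardiovascular or respiratory reaction began before, on, or after the edema onset date.
- **(c) 7% weight gain (8.2.3.3):** limit the other patients to those with a post-baseline weight, and show those without one separately. Report reactions per patient-days observed, or by the SAP's existing duration categories (up to 4, over 4 to 13, over 13 weeks). Give the number of reactions that began before the first recorded gain.

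Do not replace the weight-gain grouping with a split at the recorded gain date. Gain is dated only at about two visits, the last near the end of observation. In a simulation that dated gain by the recording visit, about 80% of gainers' reactions fell before that date, so most would move to the group without gain even if the gain had begun weeks earlier.

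The cost is a slightly longer table, SAP wording and modest programming. Reaction onset dates (Protocol 6.8), weight dates (6.4) and dosing periods (6.2) are already recorded, so no new data are needed.
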